**Additional Assessments During Laboratory Sessions (completed at -30, +15, +30, +45, +60):**

- The subjective effects battery will consist of Visual Analog Scales and the Opioid Craving Questionnaire (Tiffany et al., 1993),
- Two cognitive tasks will be used in the proposed studies. The Digit Symbol Substitution Task (McLeod et al., 1982) and the Divided Attention Task assesses attention (DAT; Miller, 1987).
- Brief Psychiatric Rating Scale (BPRS) will be performed at +45

At the end of the test testing session, the participant may receive a rescue dose of oral morphine (30 mg). If COWS scores remain >5 at the next measurement timepoint (+15 minutes) an additional 20 mg may be provided, at the discretion of a study physician. The testing session may also be terminated 20 minutes following naloxone administration (if withdrawal is too severe (COWS >20) and the rescue dose given at this time. A physician, nurse practitioner, or nurse will be notified once the COWS score goes above 9.

The RA will notify the physician/nurse practitioner once the criterion for the morphine rescue has been met, who will then administer the rescue dose. If a morphine rescue is given, vital signs will continue to be monitored for the entire 4-hour period. If a participant receives a rescue dose during the testing session, the 1 pm morphine dose may be held at the discretion of the physician.

Suicidality and Pregnancy will be monitored weekly throughout the inpatient period using the CSSRS and a urine pregnancy test, respectively.

**Discharge:** On the day of discharge, All participants receive counseling on opioid overdose risk and prevention, and receive an overdose response kit that includes 2 doses of the overdose reversal agent naloxone. Prior to discharge, all participants (completers and dropouts) will receive education concerning the various pharmacological treatment options for opioid use disorder. We strongly encourage participants to consider buprenorphine, methadone, or naltrexone maintenance and explain the benefits of these treatments in our discharge procedure. Prior to discharge from the inpatient unit, subjects who express interest in treatment will be given the opportunity to receive sustained-release naltrexone or titration onto a modest dose of buprenorphine/naloxone (prior to leaving the unit), with referral to a local treatment provider. If they refuse both of these options, they will be given a supply of buprenorphine/naloxone for up to 7 days. Bup/naloxone may also be given if a participant needs a bridge between discharge and entering treatment.

---

Follow-up: Participants will be asked to return to the laboratory 1 month after study completion to assess general health and drug use. The follow-up visit may be conducted virtually.

I attest to follow the COVID-19 Safety Guidelines for Columbia Psychiatry and NYSPI Re-Entry outlined in the NYSPI Director's June 1st memo, which include but are not limited to:

- Infection Control/PPE – Guidelines
- Research participants will only come on-site if absolutely necessary for study procedures.
- No volunteers/externs on-site during Stage 1.
- Clinical research teams will screen their participants for COVID symptoms (night before and day of onsite visit, documenting this in the chart), and escort them in and out of the building.
- COVID/COVID-like symptoms in participants will be reported to the IRB via PRISM as an SAE.

Dose Escalation Safety Pilot.

To help ensure the safety of the higher doses of vaped marijuana, the first three participants will receive V-MJ and naloxone in a dose-escalating order. The V-MJ 0 mg + naloxone 0 mg, and V-MJ 0 mg + naloxone 4 mg dose combinations will be inserted randomly in the sequence below.

- V-MJ 12.5 mg + 0 mg Naloxone,
- V-MJ 25 mg + 0 mg Naloxone,
- V-MJ 12.5 mg + 4 mg Naloxone,
- V-MJ 25 mg + 4 mg Naloxone.

A physician or nurse practitioner will provide close monitoring of each session from the adjacent observation room, or within the testing room itself. A summary of the findings from these first three participants will be reported to the IRB -on a case-by-case basis- before moving forward to the randomized dosing described above. Participants' plans to initiate treatment for opioid use disorder will also be included in our report to the IRB.

Suicide Risk Management Plan

The Columbia-Suicide Severity Rating Scale (C-SSRS) will be used to quantify the severity of suicidal ideation and behavior. The C-SSRS is only administered by study staff who have been trained in its administration. During screening and follow-up, the C-SSRS is used to assess for suicidal ideation. If there is expression or suspicion of suicidality outside of these two timepoints, the C-SSRS will first be administered, and action taken accordingly, as outlined below. If a participant endorses active suicidal ideation/behavior, staff will notify an Opioid Research Laboratory psychiatrist ([name]) or clinical psychologist (Drs [name] or [name]), who will conduct a brief, standardized clinical interview that reviews the C-SSRS score and quantifies the specific suicidal plans and access to lethal means (e.g., firearms). If the Opioid Research Lab clinicians are unavailable, the RA is instructed to contact another Division clinician. The Substance Use Research Center maintains an "on-call" list of NYS licensed psychologists and psychiatrists who are "on duty" for the day to provide clinical coverage. This list is posted in the Opioid Lab research spaces, and available in our Lab's Google Drive.

---

For participants who are deemed at imminent risk of harm to self or others, the clinician will arrange a transfer to the closest Emergency Room (ER). The clinician will speak with the responsible ER physician to provide all relevant information and request follow-up on disposition. For participants with non-active suicidal ideation/behavior (i.e., not at imminent risk), the clinician will complete the Stanley-Brown Safety Plan [Stanley B, Brown GK. Safety Planning Intervention: A Brief Intervention to Mitigate Suicide Risk. Cognitive and Behavioral Practice. 2012;19(2):256-264].

In either above scenario, study staff will also inquire if the participant is currently receiving mental health treatment, and if so, she/he will attempt to contact the participant's mental health provider. If the participant is not currently receiving mental health care, they will be provided with referrals to a qualified mental health provider. Finally, the study staff and clinician will extensively document the safety steps that were taken, the referral process, and follow-up events, in the participant's chart.

When Opioid Lab clinicians are unavailable, clinical staff on 4-South will manage suicide risk and other clinical issues that may arise with study participants. However, 4-South staff are informed to notify an Opioid Lab clinician of any important clinical issues that arise with our participants. The inpatient unit is provided with a nights and weekends "on-call," which includes the cell phone number of the physician to be contacted in such situations.

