	Admission	Stabilization	Stabilization	Stabilization	Stabilization	Stabilization	Stabilization	Stabilization	Stabilization	Stabilization	NLX 0mg + V-MJ 0mg	NLX 4mg + V-MJ 25mg		
Week 3							Week 4							
	NLX 0mg + V-MJ 12.5mg	NLX 0mg + V-MJ 25mg	NLX 4mg + V-MJ 12.5mg	NLX 4mg + V-MJ 0 mg			Discharge							

**Laboratory Testing:** Laboratory testing sessions will consist of a modified naloxone challenge procedure (A.K.A. Wang Test: Wang et al., 1974). The challenge begins with baseline assessments. Ten common symptoms of opioid withdrawal (gooseflesh, vomiting, tremor, sweating, restlessness, lacrimation/nasal congestion, yawning, warming/cooling sensations, stomach pain, and muscle ache) will be assessed by a research assistant trained in administering the SOWS/COWS. For safety, the physician or nurse who is providing medical oversight will directly observe its administration.

Each symptom is coded as either “absent” or “present,” with between 1 and 6 points added when a symptom is observed (Table 2). Following pre-test assessments, a physician or nurse practitioner will administer the study drug combination (1000-1100 hrs). Assessments of withdrawal are made at 10-minute intervals for 50 minutes. The total withdrawal score is calculated at the end of the session. To minimize carry-over effects, sessions will be conducted at least 48 hours apart (>5 half-lives of both medications). See Table 1 for an example dosing schedule. The following dose combinations of vaped marijuana (V-MJ) and IN naloxone will be tested in random order:

- Naloxone 0 mg + V-MJ 0.0 mg
- Naloxone 0 mg + V-MJ 12.5 mg
- Naloxone 0 mg + V-MJ 25 mg
- Naloxone 4 mg + V-MJ 0.0 mg
- Naloxone 4 mg + V-MJ 12.5 mg
- Naloxone 4 mg + V-MJ 25 mg

Signs and Symptoms	Table 2: Rating Scale for Opioid Withdrawal											
	(Pre-test)		Time after first naloxone dose									
	0 min		10 min		20 min		30 min		40 min		50 min	
Signs and Symptoms	Present	Absent	Present	Absent	Present	Absent	Present	Absent	Present	Absent	Present	Absent
Gooseflesh	6	0	3	0	3	0	2	0	1	0	1	0
Vomiting	6	0	3	0	3	0	2	0	1	0	1	0
Tremor	6	0	3	0	3	0	2	0	1	0	1	0
Sweating	6	0	3	0	3	0	2	0	1	0	1	0
Restlessness	4	0	2	0	2	0	1	0	1	0	1	0
Lacrimation/ Nasal Congestion	4	0	2	0	2	0	1	0	1	0	1	0
Yawning	4	0	2	0	2	0	1	0	1	0	1	0
Feeling of Change in Temperature	3	0	1	0	1	0	1	0	1	0	1	0
Stomach Pain	3	0	1	0	1	0	1	0	1	0	1	0
Muscle Ache	3	0	1	0	1	0	1	0	1	0	1	0
Actual time of observation												
Scores												
Pupil Diameter												

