STATISTICAL ANALYSES

Data Analysis Plan: The distributions of all continuous variables will be checked for normality, and transformations will be employed (if necessary) before applying specific parametric techniques. Before performing specific analyses, we will examine all outcomes for outliers. All statistical comparisons will be two-sided and the critical level for rejection of the null hypothesis will be considered to be a p-value of < 0.05 . Where needed, False Discovery Rate Analysis will be used to adjust critical p values to control for multiple comparisons. Any comparison where homogeneity is violated will not be considered significant. Means, standard deviations, proportions, and 95% confidence intervals will be used to describe all continuous variables.

Dropouts and Missing Data: As this is an inpatient laboratory study within a controlled setting, we expect only minimal intermittent missing data, though we do expect to have some subjects drop out without completing all of the experimental conditions. We will use all available data from subjects prior to drop-out. We will account for missing data directly using mixed-effects models (MEM) (Diggle et al. 2002). MEMs do not require complete measurements to estimate effects and inferences are valid provided that data are “missing at random” (Little & Rubin, 2002). ‘Missing at random’ (i.e. the missing mechanism does not depend on the value of the unobserved outcome) is un-testable in most medical research and in our study as well. One can assume either parametric or semi-parametric models for the missingness that does depend on the unobserved outcome value and do the analysis (Diggle and Kenward 1994, Kenward 1998). Comparison of the inferences from assuming various models for the missingness provides a measure of the validity of the efficacy estimate from the model that assumes missing ‘at random’. One can also compute a local sensitivity index which measures the change in the estimated treatment effect in a neighborhood of the ‘missing at random’ model for missingness (Rotnitzky et al. 1998). We will perform sensitivity analyses based on these two approaches to assess the effect of the assumption of missing ‘at random’ on the inference.

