Randomization: Once a participant is enrolled, a randomization sequence table will be generated by a blinded statistician. The table will determine the order of testing of the various dose combinations of dronabinol (.00, .35, and .70 mg), and naloxone (0.0, 0.2 and 0.4 mg).

Aims, Outcome Measures, and Hypotheses

Primary Aim: Assess the ability of inhaled dronabinol to alter the severity of naloxone-precipitated withdrawal.

- The primary dependent variable (DV) for this aim will be the total opioid withdrawal score from the testing session. Repeated-measures analysis of variance (ANOVA) will be used to assess differences among the various dose conditions.
- We hypothesize that there will be a dose-dependent effect of dronabinol to attenuate the severity of naloxone-precipitated withdrawal.

Secondary Aim: Assess the safety of inhaled dronabinol in combination with naloxone.

- The primary DVs are the SAFTEE (AEs not related to withdrawal) and physiological parameters. Generalized mixed-effects models with participant as a random effect and an autoregressive correlation structure for the within-participant observations will be used to analyze the total number of AEs and their severity.
- We hypothesize that dronabinol, in combination with naloxone, will produce more AEs than placebo but less than naloxone alone.

Secondary Aim: Assess the impact of inhaled dronabinol on naloxone's effects on pupil diameter (i.e., μ -opioid receptor blockage).

- The primary DV will be pre-to-post- medication change in pupil diameter from each testing session. Repeated-measures ANOVA will be used to assess differences among the various dose conditions.
- We hypothesize that dronabinol will not significantly alter naloxone's effects on pupil diameter (in comparison to placebo).

Secondary Aim: Assess the abuse potential of inhaled dronabinol.

- The primary DV will be pre-to-post- medication change in positive subjective drug ratings such as drug "Liking" and "Good Effect."
- We hypothesize that self-reported dronabinol "Liking" will not be significantly greater than placebo.

Power

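### If the first three, non-randomised participants are analysed, an ANOVA without a session term leaves a small order shift in the V-MJ 25 mg contrast under naloxone

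*Protocol*

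**What the plan says.** The Protocol (Study Procedures, Laboratory Testing) lists six combinations of V-MJ (0, 12.5, 25 mg) and naloxone (0, 4 mg) and says: "The following dose combinations of vaped marijuana (V-MJ) and IN naloxone will be tested in random order".

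The Dose Escalation Safety Pilot, later in Study Procedures, makes an exception: "the first three participants will receive V-MJ and naloxone in a dose-escalating order". The fixed sequence, written as V-MJ + naloxone in mg, is 12.5 + 0, 25 + 0, 12.5 + 4, 25 + 4. The remaining two, 0 + 0 and 0 + 4, are not fixed: these "dose combinations will be inserted randomly in the sequence below". Findings from the three go to the IRB "before moving forward to the randomized dosing described above", so the Protocol itself places them ahead of the randomised stage.

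The SAP (Randomization) has no such exception: "Once a participant is enrolled, a randomization sequence table will be generated by a blinded statistician", and "The table will determine the order of testing of the various dose combinations". It names no method for balancing orders. For the primary aim it says: "Repeated-measures analysis of variance (ANOVA) will be used to assess differences among the various dose conditions". No session, period or sequence term appears anywhere in the SAP. The autoregressive structure in the adverse-event model describes correlation, not an order effect.

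Neither document says whether the first three count towards the 16 completers or are analysed with them. The nearest statement, in the SAP's section on dropouts, is "We will use all available data from subjects prior to drop-out".

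**The concern.** In a six-session crossover, a change in response from session to session is separated from the treatment effect by randomising order, by modelling session, or by both. For the first three participants order is largely fixed, and the model has no session term. The naloxone 4 mg + V-MJ 25 mg condition is always last of the four active V-MJ conditions, so it tends to fall late and to follow more naloxone sessions than its comparator. If withdrawal scores drift down over the stay, part of that fall would be read as a V-MJ benefit, in the direction of the dose-dependence hypothesis. If they drift up, a real benefit would be partly hidden.

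Some drift is plausible from the Protocol. It enrols only people whose street opioid use exceeds the morphine maintenance dose, and it warns of reduced tolerance at discharge. It also names carry-over as a concern while giving two intervals between sessions: 24 hours in the Lay Summary and at least 48 hours in Study Procedures. The example schedule in Table 1 appears to use consecutive days. Those passages must be reconciled.

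**Working it through.** **Inputs from the documents.** Three participants with an escalating order and two randomly inserted conditions (Protocol, Dose Escalation Safety Pilot); 16 completers, a 15-point target and SD 20 (SAP, Power); two-sided 0.05 (SAP, Data Analysis Plan).

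**Assumptions.** All three are analysed among 16. The SD of 20 is that of the paired difference. Drift is linear, 0 to 5 points per session in either direction; the documents give no value.

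**Scale.** The plan's effect size reproduces: 15/20 = 0.75. The standard error of a paired difference is 20/√16 = 5.0 points. (The SAP's 90% power does not reproduce two-sided; a paired t-test gives 80.1%. That is a separate matter.)

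**Step 1: session position in the first three.** Four conditions in fixed relative order and two inserted at random give 6!/4! = 30 possible orders. The k-th fixed condition has mean position k × 7/5, and each inserted condition has mean 3.5.

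| V-MJ + naloxone (mg) | Mean session |
|---|---|
| 12.5 + 0 | 1.4 |
| 25 + 0 | 2.8 |
| 0 + 0 | 3.5 |
| 0 + 4 | 3.5 |
| 12.5 + 4 | 4.2 |
| 25 + 4 | 5.6 |

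**Step 2: earlier naloxone sessions.** The 0 + 4 session precedes 12.5 + 4 in 3/5 of the orders and precedes 25 + 4 in 4/5. Mean prior naloxone 4 mg sessions are therefore:
- 25 + 4: 1 + 0.8 = 1.8
- 12.5 + 4: 0.6
- 0 + 4: 0.4 + 0.2 = 0.6

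**Step 3: average over 16 completers.** Multiply by 3/16.
- 25 v 0 mg under naloxone: (5.6 − 3.5) × 3/16 = 0.39 session, and (1.8 − 0.6) × 3/16 = 0.23 prior naloxone session.
- 25 v 12.5 mg under naloxone: (5.6 − 4.2) × 3/16 = 0.26 session.
- 12.5 v 0 mg under naloxone: (4.2 − 3.5) × 3/16 = 0.13 session, and no difference in prior naloxone sessions.

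**Step 4: bias, 25 v 0 mg under naloxone.** Bias = 0.394 × drift. Drift 0 gives 0; drift 2 gives 0.8 points (5% of 15); drift 5 gives 2.0 points (13% of 15).

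**Step 5: the randomised participants.** The position difference between two conditions in one random order has mean 0 and SD √7 = 2.65. Over 13 such participants, its contribution to the 16-person mean has SD 2.65 × √13/16 = 0.60 session. This is noise, not bias. It does cost precision: if all 16 had random orders and drift were 5, the paired-difference variance would be 400 + 25 × 7 = 575 (SD 24.0). Simulated power of a paired t-test for 15 points then falls from 80% to 65%.

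**Step 6: effect of a session term.** Simulation of 3,000 trials with 3 escalating and 13 random orders, for 25 v 0 mg under naloxone. Negative drift favours V-MJ.

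| Drift | Session term | Bias | Two-sided false rejection | False rejection favouring V-MJ | Power, 15 points |
|---|---|---|---|---|---|
| 0 | none | 0.05 | 4.8% | 2.2% | 83% |
| 0 | linear | 0.03 | 5.1% | 2.4% | 83% |
| 0 | categorical | 0.03 | 4.7% | 2.2% | 81% |
| −2 | none | −0.85 | 5.9% | 3.7% | 86% |
| −2 | linear | −0.05 | 5.3% | 2.4% | 84% |
| −2 | categorical | −0.04 | 5.5% | 2.7% | 82% |
| −5 | none | −2.03 | 6.9% | 5.6% | 82% |
| −5 | linear | −0.08 | 5.1% | 2.4% | 84% |
| −5 | categorical | −0.11 | 4.9% | 2.2% | 82% |

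Simulation error is about 0.09 point on bias (5/√3000) and 0.3 to 0.4 percentage points on rejection rates. A simpler paired t-test simulation gives 3.5% and 4.7% false rejection favouring V-MJ at drifts of −2 and −5. The standard error is 5.00 without the term, 5.04 with a linear term (+0.8%) and 5.19 with a categorical term (+3.8%).

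**The case against.** The case for leaving the plan alone has several sound parts.

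- **Pooling is not stated.** The section is labelled a safety pilot, and the sentence on available data concerns dropouts, so three of 16 is an upper bound. With 16 completers projected from 32 enrolled, a 50% completion rate among the three would give 2.1 × 1.5/16 = 0.20 session and a bias of 0.4 to 1.0 points at drift 2 to 5. This stands, and is why the shift is given as a maximum.
- **Random orders do not confound.** A reader might infer that V-MJ dose is confounded with order throughout the trial. The documents do not support that: the systematic part comes only from the first three. Nor do they say that the other orders are unbalanced. The SAP gives no method, and silence is not a statement that there is no balancing.
- **Dose does not simply track session number.** Averaged over naloxone, the mean positions for 0, 12.5 and 25 mg are 3.5, 2.8 and 4.2. Without naloxone both active doses come before placebo. Under naloxone, 12.5 v 0 mg is barely shifted and has no excess of earlier naloxone sessions.
- **Participants should be stable before testing.** The Protocol requires 5 to 14 days on morphine, then a mean COWS of no more than 5 without hydromorphone, and everyone has had a naloxone challenge at screening. This weakens the argument for drift. It does not exclude a change in precipitated withdrawal over repeated challenges.
- **The SAP text is out of date here.** Its randomization paragraph still names inhaled dronabinol and different naloxone doses, so its silence on the escalation may be an update not made. That explains the gap but does not close it.

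What remains is a non-randomised order in three people whose analysis status is open, and a model that cannot absorb an order effect.

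**Conclusion.** The point holds as a modest, conditional one. If the first three are analysed, the 25 v 0 mg contrast under naloxone carries a systematic lag of at most 0.39 session. At an assumed drift of 0 to 5 points per session, the bias is 0 to 2.0 points against the 15-point target and a standard error of about 5. Its direction is unknown. Drift of 2 to 5 points favouring V-MJ would raise false rejection in its favour from 2.5% to about 4% to 5.5%.

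A reader might conclude that the primary result will be biased. That does not follow: it needs both pooling of the first three and real drift, and the documents establish neither. The case for acting is that a session term removes the possible bias, recovers precision if drift exists, and costs very little if it does not.

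**What to change.** 1. Add session number (1 to 6) as a fixed effect in the primary model and in the secondary models that compare dose conditions. Cost: one degree of freedom if linear or five if categorical, and a standard error about 1% to 4% larger if there is no drift.
2. State in the SAP that the first three had a non-randomised escalating order with two conditions inserted at random, and whether they are in the primary analysis and count towards the 16. Cost: wording only.
3. Repeat the primary analysis without the first three as a stated sensitivity analysis. Cost: one extra run, with lower precision in that run.

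Optional: name a balanced scheme, such as Williams sequences for six conditions, for participant 4 onward. Thirteen is not a multiple of six and dropouts will disturb balance, so it would reduce chance imbalance without removing it; the session term already deals with the bias.

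These changes need no extra participants or visits and leave the safety escalation as it is. They should be fixed before outcome data are examined.
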